Influence of Multiple Ratio Split-belt Treadmill on Gait Asymmetry and Motor Learning in PD patients with Freezing of Gait

I. General information

Version and date of protocol: version 5, 14/11/2017

Funder: Jacques and Gloria Gossweiler Foundation, Switzerland

Sponsor/Research Unit: Research Group for Neuromotor Rehabilitation, Faculty of Kinesiology and Rehabilitation Sciences, KU Leuven

Principal investigator: [name]
[name]
[contact]
E-mail: [contact]

Sub-investigator: [name]
[name]
[contact]
E-mail: [contact]

Study period: 01/11/2017 – 31/10/2018

Signatures

The undersigned confirm that the following protocol has been agreed and accepted and that the Principal Investigator agrees to conduct the trial in compliance with the approved protocol and will adhere to the principles outlined in the requirements for the conduct of clinical trials in the EU as provided for in "Directive 2001/20/EC", and any subsequent amendments, GCP guidelines, the Belgian law of May 7th 2004 regarding experiments on the human person, the Sponsor's SOPs, and other regulatory requirements as amended.

I agree to ensure that the confidential information contained in this document will not be used for any other purpose other than the evaluation or conduct of the clinical investigation without the prior written consent of the Sponsor.

I also confirm that I will make the findings of the trial publically available through publication or other dissemination tools without any unnecessary delay and that an honest accurate and transparent account of the trial will be given; and that any discrepancies from the trial as planned in this protocol will be explained.

Principal Investigator (KU Leuven)

[name]

11th October 2017

.....
Name & Title

.....
Signature

.....
Date

Principal Investigator (participating site University Kiel)

[name]

12th October 2017

.....
Name & Title

.....
Signature

.....
Date

II. Dutch summary of the protocol

Titel onderzoeksproject:

Invloed van multiple ratio split-belt loopbandtraining op stapasymmetrie bij personen met de ziekte van Parkinson en gangblokkades

Deelnemers:

32 patiënten met de ziekte van Parkinson, met 'Freezing of Gait'

32 leeftijdsgematchte gezonde proefpersonen

Type studie:

Multi-centrische studie (Mono-centrisch in België) aan de Faculteit Bewegings- en Revalidatiewetenschappen

Trainingsstudie

Academische studie

Metingen:

Screeningstesten ter evaluatie van motorische en cognitieve functie bij ziekte van Parkinson

Vragenlijsten naar 'Freezing of Gait', vermoedheid en cognitie

Klinische meetsschalen ter evaluatie van evenwicht en van de ernst van de 'Freezing of Gait'

5 m stappen buiten de loopband met en zonder een dubbeltaak

Training protocol:

Loopbandtraining van 6 x 5 min. Met telkens 1 min. zittende pauze

Duur experiment:

Patiënten met Parkinson en Freezing of gait: 2 sessies van 2 uur op 2 aparte testdagen

Gezonde controles: 2 sessies van 2 uur op 2 aparte testdagen

Plaats van de experimentele sessies:

Faculteit Bewegings-en Revalidatiewetenschappen, KULeuven

III. Background and rationale

Parkinson's disease (PD) is the **second most common** neurodegenerative disease [1, 2]. It has a substantial impact on patients' quality of life as well as on the socio-economic cost for society [3]. Gait problems are very prevalent in PD and markedly reduce patients' functional independence [4]. Freezing of gait (FOG) is without doubt the most disabling gait impairment and it constitutes **an independent risk factor for falls** [5]. This complex symptom is defined as an episode of substantial reduction or complete cessation of movement despite having the intention to move [6]. Current medical and surgical treatments only partly relieve FOG [7], strongly suggesting that non-dopaminergic mechanisms mediate its occurrence [8]. Therapeutic alternatives are, therefore, **urgently needed**. A growing body of literature

suggests that exercise and **motor learning can significantly improve gait** and mobility in PD [9, 10] with long term effects ranging from 4 to 48 weeks [11].

FOG occurs when spatiotemporal motor control breaks down and is associated with gait cycle variability, **reduced stride amplitude** and hastening of gait timing. Furthermore, FOG is also related to between-limb coordination deficits and **gait asymmetry** [12-14]. The strong link between FOG and gait asymmetry [14, 15] is underscored by the fact that turning – which is a highly asymmetric task, is the most important trigger of FOG [16, 17].

Split-belt treadmill walking, whereby the walking speed of each leg can be manipulated independently, is a useful tool to study both motor switching and modulating gait asymmetry. In a recent study at our lab, motor switching ability during different asymmetric split-belt conditions was studied in patients with and without FOG. It was shown that non-freezers were **able to adapt spatial gait symmetry** to different switching split-belt conditions similarly as healthy controls. However, **adaptive capacity was reduced in freezers** (figure 1A) [18]. The powerfulness of the split-belt paradigm was also confirmed by the fact that immediately after the switch, FOG was evoked in two cases. In another study from the group at Christian-Albrechts University Kiel (CAUK), Germany, the **short-term effects of 10 minutes split-belt walking** were studied through reducing the belt velocity of either the body side with the longer or shorter step length in PD. **Gait asymmetry, bilateral coordination and the consecutive reduction in step lengths were improved** in the tied-belt condition after subjects walked with reduced velocity at the side with the longer step length ("better side reduction") (figure 1B) [19]. These exciting pilot results provide **proof-of-principle evidence** for the current project. To consolidate these findings, our research group in collaboration with the group at Kiel will undertake two studies, probing short term motor adaptation (present study) and prolonged motor learning (future study) to alleviate freezing-related gait deficits.

[figure not shown]

Figure 1. A) Impaired adaptive capacity of patients with PD with FOG during split-belt gait (data from KUL: mod. according to Mohammadi et al. 2015); B) Step length during baseline, early and late split-belt adaptation (25% reduced belt's speed of the leg with the longer step length (best-side reduction)) and after effect (data from CAUK: mod. according to Fasano et al. 2016).

IV. Study objectives

Motor adaptation refers to behavioural changes induced by new environmental dynamics, commonly studied by inducing an unfamiliar perturbation into an otherwise familiar task. Here, split-belt speed manipulations will be used **to study implicit motor adaptation**, i.e. without raising conscious attention to the adaptive behaviour nor demanding an explicit strategy [18]. Motor adaptation plays an important role in **the acquisition (early) phase of motor learning**, the hallmark of which is reaching a stable level of performance. In contrast, the late consolidation phase of motor learning is characterized by: 1) **automatization**, or the ability to withstand dual task interference; 2) **transfer**, or the ability to generalize to untrained circumstances and 3) **retention**, or the ability to sustain improvements after a period without practice. [20]. Our previous work has shown that despite disease-related damage, **patients with PD can still reconfigure neural networks** to optimize motor control and achieve partially consolidated motor learning gains [21]. Interestingly, from recent study on manual tasks, it appears that **variable practice** (random versus blocked) and practice requiring greater adaptation (with versus without contextual interference) led to **worse immediate performance but better learning retention** in PD and older adults. This strongly suggests that in order to enhance better storage in motor memory and automatic retrieval of practice gains, **practice conditions are critical**. In this project, we want to study these phenomena for the first time during gait. More specifically, we want to know how PD impacts upon maintenance of stride amplitude when adapting to varying split-belt conditions in order to achieve robust learning.

Research Questions and Hypothesis

We aim to investigate two research questions:

We intend to better understand the impact of PD on the **adaptive response to different split-belt conditions** relative to healthy age-matched controls.

We will investigate the short-term effects of different split-belt conditions in order to determine the **optimal conditions for long-term training** in patients with FOG and test which condition leads to the best 24-hour retention.

We hypothesize that being exposed to larger contrasts between split-belt speeds (ratio) will result in improved gait symmetry and better savings in motor memory, thus leading to better retention effects and this more so in controls than in PD. We also hypothesize that variable split-belt conditions (changing ratios) will lead to better adaptive capacity to transitions than steady split-belt walking with a consistent ratio.

V. Methodology of the research

Number of participants: This pilot study investigating the short-term effects of split-belt walking on gait asymmetry and motor learning is conducted in collaboration with CAUK and will include a total number of 128 participants i.e 64 at each centre comprising 32 patients with PD and 32 healthy controls.

Recruitment: Older adults will be recruited from an existing database of healthy volunteers. Recruitment of PD patients will be conducted via a database of patients that has been built up over the years in our laboratory in collaboration with the neurologist at the Movement Disorders clinic at UZ Leuven ([name]. [name]). Flyers containing study information will be handed to people expressing interest to participate.

Inclusion and Exclusion Criteria: PD patients with FOG who can walk at least 5 minutes at a stretch will be included in this study. Exclusion criteria are: participation in treadmill training in the 3 months prior to the study, other neurological impairments, orthopedic injuries that could influence gait or balance, cardiovascular exercise risk factors, dementia or self-reported DBS-related postural or gait disturbances.

Design: Patients will be tested in the ON phase of medication on consecutive days in a session of about 2 hours. Figure 2 shows that the included subjects will be randomized into 4 treatment groups to compare the impact of different (3:4 and 1:2) and changing ratios of split-belt walking relative to traditional treadmill training (Tied-Belt). Effects will be analysed pre-post (I-II) and after 24 hours (III) retention. The second training session (III-IV) will explore the possible benefits of repeated training and serves as a pilot for a larger training study.

Standardization: Testing and training methods and protocol as well as patient instructions will be standardised across the two centres by documentation of procedures as well as through regular communication. Researchers from both groups will attend initial measurements and in addition, during the first 3 months of the project, a monthly skype call between researchers will be held to check the fidelity of procedures and ensure adherence.

[figure not shown]

Figure 2. Study design. 128 participants will be recruited across the two centres and data will be pooled for analysis. SBT, Split-belt Treadmill; PD, Parkinson's disease; HC, healthy control.

Intervention

Participants will first walk normally (5 x 5m) at a comfortable pace to assess **overground walking speed** and to assess which leg has the longer/shorter step length. **Best/worst side** will be further confirmed with a toe-tapping test and by asking the PD patients about their more/less affected PD side. Next, participants will walk on the treadmill for a maximum of 3 minutes to get familiar with treadmill walking, reaching their overground gait speed. Intervention will consist of one training session of 6 x 5 min. treadmill gait with 1 min. rest in between [12]. Participants are not allowed to walk overground during the rest but a chair will be provided if necessary. Subjects are wearing a harness to prevent falling. Belt speed will be adjusted according to the individual's comfortable overground gait velocity. Previous studies have shown **improved gait symmetry after split-belt conditions with slower belt speed of the side with the longer step length ('best side reduction')** in PD and stroke [19, 23]. As it has been shown that belt speed ratio but not absolute speed impacts on gait asymmetry (unpublished data), we chose to decrease the belt speed of the side with the longer step length rather than increasing the belt speed of the side with the shorter step length. Also, to avoid hastening, the 'best side reduction' principle will be adopted using a 3:4 or 1:2 ratios (table 1).

Table 1: Belt speed of the 4 treatment groups

Group	Belt speed ratio	Belt speed of the leg with the longer step length (% of overground gait speed)	Belt speed of the leg with the shorter step length (% of overground gait speed)
A-Steady Split-belt Treadmill	3:4	75%	100%
B-Steady Split-belt Treadmill	1:2	50%	100%
C-Transfer Split-belt Treadmill	changing	50-75%	100%
D-Treadmill (tied-belt)	1:1	100%	100%

Outcome Measures

Laboratory FOG assessment: A FOG ratio score will be calculated [24]. FOG will be analysed with accelerometer sensors (APDM) during FOG provoking tasks (360° turning in place (right/left side alternating) for 1 minute with and without a cognitive dual task.

Overground gait analysis: the following gait variables will be analysed during 5 trials of 5m gait with comfortable pace (assessed via accelerometer sensors (APDM) and Vicon/Qualisys motion capture analysis): step length, gait asymmetry, gait variability, bilateral coordination [25] and gait velocity.

Treadmill gait analysis: adaptive capacity during transitions will be assessed by analysing the above mentioned variables during changing split-belt conditions. Retroreflective markers will be placed bilaterally on the limbs to allow gait analysis at 100Hz with infrared cameras.

Descriptors: MDS-Unified Parkinson's Disease Rating Scale (MDS-UPDRS) [26], New Freezing of Gait Questionnaire [27], Mini Mental State Exam (MMSE) [28], Montreal Cognitive Assessment (MoCA) [29], Frontal Assessment Battery, Falls Efficacy Scale International (FES-I), Mini-BESTest [30], Borg Rating of Perceived Exertion, Visual Analogue Scale for fatigue and number of falls during the last 6 months.

VI. Planned Statistical analysis & Data Management

Data storage: Part of the data obtained on paper (e.g. questionnaires, informed consent forms) will be stored in an excel file. The data obtained by computerized measures will all be stored in the original digital files, and the main variables will be stored in excel datafiles. All data will regularly be backed up to a secure KU Leuven server.

Statistics: Data from both centres will be pooled for the statistical analysis. The immediate effects and short term (24 hour) retention of split-belt treadmill training on overground gait symmetry and the freezing ratio during the turning task are the **main outcomes of interest**. Repeated measures ANOVA with group and training condition as between subjects factors will be employed in order to test this. Effect sizes will be determined and a post-hoc power calculation will be performed to ascertain sample sizes for a planned larger training study.

VII. Safety

Our laboratory has vast experience with testing patients with PD. Testing will be carried out in a standard movement laboratory setting when using their normal medication. Subjects will be asked to wear well-fitting, flat-heeled and comfortable shoes for walking during the session and a safety harness will be provided while on the treadmill to avoid falls at all times. In between trials, sufficient seated rest periods will be inserted to avoid fatigue. Two experienced testers will be present at all times to ensure safety of the participants. If patients require their normal medication, this will be accommodated. No interference with normal intake is foreseen.

VIII. Costs

Full reimbursement of travel expenses for the people with Parkinson's disease and age-matched controls (i.e. the healthy elderly) will be covered by the project. There will be no additional reimbursements.

IX. Ethics

The protocol is submitted for review to the **local Ethics Committee** of the KU Leuven (Commissie Medische Ethisiek UZ Leuven, [name]). The study will be performed in accordance with The Code of Ethics of the World Medical Association (Declaration of Helsinki, 1967) and the principles of GCP. Any subsequent protocol amendments will be submitted to the Ethics Committee and Regulatory Authorities for approval.

After complete explanation of the study protocol, **written informed consent** will be obtained from all participants prior to participation in the experiment.

The investigators will treat all information and data relating to the study **confidentially** and will not distribute this information to third parties or use it for any other purpose than the current study. Data will be coded and will be protected from disclosure outside the research environment.

The collection, processing and disclosure of personal data, such as patient health and medical information is subject to compliance with applicable personal data protection and the processing of personal data (Directive 95/46/EC and Belgian law of December 8, 1992 on the Protection of the Privacy in relation to the Processing of Personal Data).

X. Insurance

In accordance with the Belgian Law relating to experiments on human persons dated May 7, 2004, **Sponsor shall assume, even without fault, the responsibility of any damages** incurred by a Study Patient and linked directly or indirectly to the participation to the Study, and shall provide compensation therefore through its insurance. **Sponsor delegates** his insurance duty (pursuant to art 29 of the Belgian Law relating to experiments on human persons dated May 7, 2004,) **for participants in other countries than Belgium** to the respective participating site(s) of that country, who hereby accept(s).

References

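### The walk that picks the longer-step leg may also be the pre-test; if asymmetry is signed by that leg, it falls after baseline without any training effect

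*Protocol*

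**What the plan says.** **Selection of the leg.** Under Intervention, "Participants will first walk normally (5 x 5m) at a comfortable pace to assess" overground speed "and to assess which leg has the longer/shorter step length". The side "will be further confirmed with a toe-tapping test and by asking the PD patients about their more/less affected PD side". Patient report is therefore available in PD only, and no rule covers disagreement between the three sources. Table 1 then sets belt speeds by longer-step and shorter-step leg.

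**Outcome walk.** Under Outcome Measures, for overground gait, "the following gait variables will be analysed during 5 trials of 5m gait with comfortable pace". Step length and gait asymmetry are among those variables. Number of trials, distance and pace match the selection walk.

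**Contrasts.** The Design paragraph states: "Effects will be analysed pre-post (I-II) and after 24 hours (III) retention". It also says the split-belt ratios are compared with tied-belt training.

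**Analysis.** Section VI names overground gait symmetry as a main outcome, at once and after 24 hours, and plans "Repeated measures ANOVA with group and training condition as between subjects factors". It adds that effect sizes will be determined and used towards sizing a larger study, without saying which effect sizes.

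**Hypothesis.** Section IV expects larger belt-speed contrasts to improve symmetry and retention, "and this more so in controls than in PD".

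**The concern.** A leg picked because it had the longer step on one noisy walk is picked partly on noise. If the same walk supplies the baseline, an asymmetry value signed by that leg is positive by construction and too large on average. At the next test the noise is fresh, so the signed value falls towards its true level with no intervention at all.

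The fall looks like improved symmetry. A tied-belt comparison removes it, because every randomised arm is selected in the same way. It is not removed from change within an arm or a pooled group, or from the comparison of PD with controls over time, which randomisation does not protect and which addresses the first research question. Any effect size for the larger study drawn from those quantities would carry the same error.

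**Working it through.** **Inputs from the protocol.** Total 2 centres x (32 PD + 32 controls) = 128, which matches the stated number. PD and controls are 64 each. With four equal conditions there are 64 / 4 = 16 per group-by-condition cell. There is no power calculation to reproduce.

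**Assumptions (not in the protocol).** True left-right asymmetry D ~ N(0, tau²); independent walk error e ~ N(0, s²) at each test; leg chosen by the walk alone; no true change; two-sided 5% tests on change scores. Reliability is rho = tau² / (tau² + s²).

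**Formula.** The signed pre-test is |D + e1| and the signed later value is sign(D + e1) x (D + e2).

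- Expected fall = sqrt(2/pi) x s² / sqrt(tau² + s²).
- As a share of the mean pre-test value, this is s² / (tau² + s²) = 1 - rho.

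**Size of the fall, s = 1:**

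| tau | rho | fall | % of pre-test |
|---|---|---|---|
| 0.5 | 0.20 | 0.71 | 80% |
| 1 | 0.50 | 0.56 | 50% |
| 2 | 0.80 | 0.36 | 20% |
| 3 | 0.90 | 0.25 | 10% |

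For example, at tau = 1: 0.798 x 1 / sqrt(2) = 0.56. Simulation agrees with the closed form.

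**Spurious effect size.** The SD of the change is sqrt(2s² - fall²). The standardised change is therefore 0.25 / sqrt(2 - 0.25²) = 0.18 at rho 0.9, 0.36 / sqrt(2 - 0.36²) = 0.26 at 0.8, and 0.56 / sqrt(2 - 0.56²) = 0.43 at 0.5.

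**Simulated false-positive rates for pre-post change (nominal 5%):**

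| rho | one cell, n = 16 | pooled group, n = 64 |
|---|---|---|
| 0.9 | 10% | 30% |
| 0.8 | 17% | 53% |
| 0.5 | 37% | 94% |

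**PD versus controls over time, 64 v 64:**

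| Controls (tau, s) | PD (tau, s) | fall, controls | fall, PD | false positives |
|---|---|---|---|---|
| 1, 1 | 2, 1 | 0.56 | 0.35 | 15% |
| 0.5, 1 | 2, 1 | 0.72 | 0.36 | 33% |
| 1, 1 | 2, 1.5 | 0.56 | 0.72 | 9% |
| 1, 1 | 2, 2 | 0.56 | 1.12 | 34% |

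The direction reverses between rows two and three. Over the tau pairs tried, the two falls are equal when the PD error SD is 1.16 to 1.54 times that of controls.

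**What is not affected.** In the same signed scenarios, comparisons between randomised conditions reject in 4.5% to 5.2% of trials, and the group x condition x time contrast averages about 0. With an unsigned index, or with the leg chosen on a separate walk with independent error, the mean fall is about 0 and the time and PD/control-by-time rates return to 4.6% to 5.9%.

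**The case against.** The strongest reply is that the artefact needs two things the protocol does not state: that the selection walk is assessment I, and that asymmetry is signed by the selected leg. Table 1 sets belt speeds; it is not an outcome formula. Figure 2, which may show the timing of I to IV, could not be read in the copy at hand. An index formula may properly sit in a SAP. All of this stands, so the point is conditional. It is still worth making, because the two walks have the same format, the treatment itself is framed by the longer-step leg, and how the walks are collected is fixed in the protocol.

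It also stands that toe-tapping and patient report might overrule the walk in some participants. That would shrink the fall, which is why (1 - rho) is an upper figure under this model. Without a rule for disagreement the reduction cannot be quantified.

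A further reply is that the Design paragraph already compares ratios with tied-belt training and that no within-arm test at n = 16 is specified. This is correct: the n = 16 rates describe a reading of the pre-post data, not a named test. The ANOVA does, however, carry the PD/control factor over time.

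A reader might infer that controls must fall more, and that the plan is therefore biased towards its own hypothesis. The documents support neither step. Controls fall more if their true asymmetry is smaller and measurement error is similar in both groups. Section III links freezing with gait variability, so larger error in PD is possible and would reverse the order. The hypothesis concerns larger belt-speed contrasts helping controls more, which is a group x condition x time question, and that contrast is unbiased.

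**Conclusion.** The concern holds in conditional form. If the selection walk doubles as assessment I and asymmetry is signed by the selected leg, asymmetry falls at II and III by up to (1 - rho) of baseline without any training effect: 10% at rho 0.9, 20% at 0.8, 50% at 0.5. Reliability is assumed, not given. The quantities exposed are uncontrolled pre-post change, the PD-versus-control change over time (in either direction), and effect sizes drawn from these. The randomised comparisons are sound, and an unsigned index does not show this fall. The matter should be settled in the protocol, with medium confidence, because the preventive step is cheap.

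**What to change.** 1. **Intervention section.** State whether the selection walk is assessment I. Then either choose the leg on a first 5 x 5 m set and take assessment I from a second set recorded afterwards, or specify an unsigned asymmetry index. A second set costs 5 x 5 = 25 m of walking. It does not remove error shared within a day: with day-level variance d², the signed I-III value still falls by d² / (tau² + d²) of the pre-test mean. The tied-belt contrast below covers that remainder.

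2. **Section VI.** Estimate I-II and I-III effects on asymmetry as contrasts with the tied-belt arm, within PD and within controls, with pre-test asymmetry as covariate. State that within-arm change and the plain PD/control-by-time term are not read as training effects. Take effect sizes for the larger study from the arm contrasts. This makes explicit a comparison the Design paragraph already intends. Compared with change scores, the covariate lowers residual variance by 4% (rho 0.8) to 11% (rho 0.5) for a signed index, and by 20% to 39% for an unsigned one. The cost is wording only.

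### The pooled two-centre ANOVA names no centre factor, so any centre difference in change stays in the error term of the training-condition contrasts: a minor, nearly free precision loss

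*Protocol*

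**What the plan says.** Section V (Number of participants) sets the sample at 128, with "64 at each centre comprising 32 patients with PD and 32 healthy controls". The Design paragraph says that "included subjects will be randomized into 4 treatment groups" and points to Figure 2 for the scheme; the figure is not reproduced in the text at hand. The same paragraph defines the effects as change from test I to test II and retention at test III, 24 hours later.

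Section VI (Statistics) says "Data from both centres will be pooled for the statistical analysis" and gives the model: "Repeated measures ANOVA with group and training condition as between subjects factors will be employed in order to test this". The main outcomes are overground gait symmetry and the freezing ratio during turning. The paragraph adds that effect sizes and a post-hoc power calculation from this study will be used to size a larger training study. Centre does not appear in the model sentence.

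**The concern.** With two centres pooled, participants can differ in change for reasons tied to the centre: who was recruited, how training was delivered, or how tests II and III were run. With only diagnosis and training condition in the model, such a difference counts as unexplained variation between participants.

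Two things are then affected. The contrasts among the four training conditions lose precision, and these contrasts are meant to identify the best condition for long-term training. The standardised effects carried into the larger study are also divided by an SD that includes removable centre variance, so they come out too small.

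Two parts of the analysis are not exposed. A constant offset between centres is present at every visit and drops out of within-person change. PD versus control cannot be confounded with centre, because both centres enrol 32 of each.

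**Working it through.** **The Protocol's figure.** 2 centres × (32 PD + 32 controls) = 128, as stated. No alpha, power, SD or effect size accompanies it, so there is no power calculation to reproduce.

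**Inputs.**
- From the Protocol: 64 PD patients, 32 per centre, and four training conditions.
- Assumed: equal arms, so 64/4 = 16 PD patients per arm. Stratified allocation would give 32/4 = 8 per arm per centre.
- Assumed: a centre difference in mean change of *d* within-centre SDs of change, with *d* = 0.5 or 1.0.

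**Error variance without a centre term.** With half the patients in each centre, the variance of change is 1 + *d*²/4 in units of the within-centre variance.
- *d* = 0.5: 1 + 0.25/4 = 1.0625; SD factor √1.0625 = 1.031.
- *d* = 1.0: 1 + 1/4 = 1.25; SD factor √1.25 = 1.118.

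**Standard error of a contrast between two PD arms.**
- Centre in the model, balanced arms: √(2/16) = 0.354.
- No centre term, *d* = 0.5: √(2 × 1.0625/16) = 0.364, about 3% larger.
- No centre term, *d* = 1.0: √(2 × 1.25/16) = 0.395, about 12% larger.

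**Power.** A true difference of 0.99 SD has power 0.80 with SE 0.354 (0.9905/0.3536 = 2.80 = 1.96 + 0.84). Dividing 2.80 by 1.031 and 1.118 gives 2.72 and 2.51, so power is 0.78 and 0.71.

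**Effect sizes carried forward.** A standardised effect shrinks by 1/1.031 = 0.97 or 1/1.118 = 0.89. Required sample size goes with the inverse square of the effect, so it rises by 6% or 25%.

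**Chance imbalance is the same loss seen from another side.** If allocation ignored centre, the difference in centre share between two arms of 16 would have SD 0.178. At *d* = 0.5 this moves the contrast with SD 0.5 × 0.178 = 0.089. Then √(0.354² + 0.089²) = 0.365, which matches the 0.364 above. The two figures must not be added together.

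**Check by simulation on change scores.** Assumed: single-visit SD 1, correlation 0.7 between visits, 6,000 allocations per setting.
- Constant centre offset of 0 or 1 SD: the SE of the contrast is 0.273 to 0.276 in all four settings, stratified or not. The offset has no effect.
- Centre difference in change of 0.5 units: SE 0.286 to 0.288 unstratified, 0.274 to 0.275 stratified, a difference of about 5%.

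This agrees with the formula. The SD of change is √(2 × 0.3) = 0.775, so 0.5 units is *d* = 0.645, and √(1 + 0.645²/4) = 1.051.

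**Cost of the term.** The stated model has 2 × 4 = 8 between-subject cells, leaving 128 − 8 = 120 error degrees of freedom. Adding centre leaves 119.

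**The case against.** The strongest objection is that a one-sentence model in a protocol is a summary, and that an analysis plan not shown here may well add centre. That is fair, and it is why this is an improvement to a stated method and not an error. What stands is that the Protocol does more than stay silent: it announces pooling and lists the between-subject factors, and centre is not one of them.

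Several stronger readings are tempting, and the text does not support them.

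- **Allocation ignores centre.** The text describes a single randomisation into four groups, but it refers to Figure 2, which is not available. The quota of 32 per diagnosis per centre fits allocation within centre equally well. It is an open question.
- **Each centre has its own testers and camera system.** The outcome section names "Vicon/Qualisys motion capture analysis" but assigns neither system to a centre, and nothing says how testers are divided. The freezing ratio comes from body-worn sensors alone, and a fixed difference between cameras would cancel in change anyway.
- **Procedures drift after the early calls.** The Standardization paragraph says "during the first 3 months of the project, a monthly skype call between researchers will be held", but it also commits both centres to documented procedures, regular communication with no stated end, and joint attendance at initial measurements. No drift can be inferred.
- **The contrasts are biased.** Under random allocation, chance imbalance by centre is part of sampling error, and the pooled error term already carries it. The loss is one of precision only.

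It is also fair to say that the documents give no evidence of a centre difference in change, and that a pilot makes no power claim.

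**Conclusion.** The point holds as a minor one. The stated model leaves any centre difference in pre-post or 24-hour change in the error term of the training-condition contrasts and in the effect sizes that feed the larger study. The SE of a contrast between two PD arms is about 3% larger if the centres differ by 0.5 SD in change and about 12% larger at 1.0 SD. If they do not differ in change, nothing is lost. The result rests on equal arms of 16 and on assumed values of the centre difference, since the Protocol supplies none. The 1.0 SD case is an upper illustration, because it presumes a large difference in response to a standardised protocol. Validity is not in question, and the PD-versus-control comparison is not exposed to uneven centre mix.

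**What to change.** In section VI, add centre as a between-subject factor, with its interaction with time, to the repeated measures ANOVA. The interaction is the part that matters, because it removes a centre difference in change; the main effect of centre only absorbs a constant offset. Derive the effect sizes for the larger study from this model. The cost is one degree of freedom plus the interaction, with no new data.

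In section V, state how allocation treats centre. If Figure 2 does not already show it, randomise separately within the four strata (Leuven PD, Leuven controls, Kiel PD, Kiel controls), so that each arm holds 8 per stratum. The cost is four lists instead of one. The two changes do different work: stratification removes the chance imbalance, and the model term takes the centre variance out of the error.
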